14.4 European Quality of Life-5 Dimensions-3 Level Questionnaire

The EQ-5D-3L comprises a descriptive aspect and the EQ-5D-3L VAS. [Table 14-4](#) presents the descriptive aspect of the EQ-5D-3L, with the 5 domains (1 question each) of the EQ-5D-3L questionnaire. There are 3 levels of response (a score of 1, 2 or 3) to each question.

Table 14-4: European Quality of Life-5 Dimensions-3 Level Questionnaire

The EQ-5D-3L index score (the EuroQoL Group, 2015) will be derived using the UK time trade off (TTO) value set as shown in [Table 14-5](#).

The EQ-5D-3L index score will be derived as:

$$EQ-5D-3L \text{ Index Score} = 1 - (0.081 + M02 + M03 + SC2 + SC3 + UA2 + UA3 + PD2 + PD3 + AD2 + AD3 + N3)$$

where the scores associated with each abbreviation above are explained in [Table 14-5](#) below.

Table 14-5: UK TTO Value Set

Condition	Score if condition is true; else zero
Full Health (all questions have score 1)	1
At least one 2 or 3	0.081
At least one 3 (N3)	0.269

Table 14–5: UK TTO Value Set

Condition	Score if condition is true; else zero
Mobility = 2 (MO2)	0.069
Mobility = 3 (MO3)	0.314
Self-care = 2 (SC2)	0.104
Self-care = 3 (SC3)	0.214
Usual activities = 2 (UA2)	0.036
Usual activities = 3 (UA3)	0.094
Pain/discomfort = 2 (PD2)	0.123
Pain/discomfort = 3 (PD3)	0.386
Anxiety/depression = 2 (AD2)	0.071
Anxiety/depression = 3 (AD3)	0.236

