8.3.7 European Quality of Life - 5 Dimensions-3 Level Questionnaire

The EQ-5D-3L questionnaire is a standardized instrument developed as a measure of health-related QoL that can be used in a wide range of health conditions and treatments. The EQ-5D-3L consists of a descriptive system and the EQ-5D-3L VAS.

The descriptive system comprises 5 questions on the following dimensions: mobility, self care, usual activities, pain/discomfort and psychological status (anxiety/depression) with 3 possible answers for each item (1=no problem, 2=moderate problem, 3=severe problem). The scores on these 5 dimensions (domain scores) represent a health profile for the subject and can be converted to a single summary index with a maximum score of 1 using a pre-defined algorithm and table of scores. The maximum index score of 1 indicates the best health state, by contrast with the scores of individual questions from the descriptive system, where higher scores indicate more severe or frequent problems.

The EQ-5D-3L VAS records the subject's self-rated health on a vertical 0 to 100 scale, with 100 indicating the best health status.

[Section 14.4](#) shows the full questionnaire together with the derivation of the EQ-5D-3L index score (Dolan 1997).

The 5 domain scores, derived EQ-5D-3L index score and VAS scores will be listed by treatment group for each subject at each visit, including changes from Baseline for the EQ-5D-3L index score and VAS score.

The number and percentage of subjects giving each categorical response (1, 2 or 3) to the questions on the EQ-5D-3L domains will be summarized by visit and treatment group, overall and by Baseline Hurley Stage. Shifts from Baseline in the domain scores at each post-Baseline visit will also be presented by treatment group, overall and by Baseline Hurley Stage. Any questions with a missing or ambiguous response (eg, 2 boxes ticked for a single dimension) will be counted in the category "Missing" in the categorical summaries of the EQ-5D-3L domain scores.

The numeric domain scores and changes from Baseline will also be summarized by treatment group, overall and by Baseline Hurley Stage as continuous variables using summary statistics at each visit. Any questions with an ambiguous response (eg, 2 boxes ticked for a single dimension) will be regarded as missing for the tabulations.

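### The EQ-5D-3L index formula in SAP 14.4 subtracts 0.081 unconditionally, so coded as printed it gives full health 0.919 where Table 14-5 and the stated maximum give 1

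*SAP*

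**What the plan says.** SAP 14.4 states that the index "will be derived using the UK time trade off (TTO) value set as shown in" Table 14-5. It then prints a derivation line that begins "1 - (0.081 + M02 + M03 + SC2 + SC3" and adds the other item terms and N3 inside the bracket. The text says that the table explains the scores belonging to the abbreviations in that line.

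Table 14-5 is a list of conditions under the column heading "Score if condition is true; else zero". Three of its rows are not item-specific:

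- "Full Health (all questions have score 1"), with the value 1. This is an index value rather than a decrement, and the formula has no term for it.
- "At least one 2 or 3", with the value 0.081. This row carries no abbreviation.
- "At least one 3 (N3"), with the value 0.269.

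The remaining ten rows give the level-2 and level-3 decrements for the five items.

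SAP 8.3.7 says of the index: "The maximum index score of 1 indicates the best health state". Protocol 9.8 gives the same maximum. Change from Baseline in the index is a listed exploratory efficacy variable (protocol 4.1.2, SAP 2.2.1.2). SAP 8.3.7 summarizes it by visit and treatment group, overall and by Baseline Hurley Stage.

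**The concern.** A derivation in an analysis plan should give one answer, and this section gives two for the same patient. A programmer who follows the formula line subtracts 0.081 from everyone and can never obtain an index above 0.919. A programmer who follows the table obtains 1 for full health.

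The sentence linking the two does not clearly settle the matter. It refers to abbreviations. The item terms and N3 are abbreviations with matching table rows, but 0.081 stands in the formula as a bare number.

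The state in dispute is the ceiling of the scale, which a subject reaches on recovering completely. A literal coding would lower the observed index of such subjects and shrink their change from Baseline.

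**Working it through.** **Inputs, all from SAP 14.4, Table 14-5.** Constant 0.081 (if any answer is 2 or 3); N3 0.269 (if any answer is 3). Decrements for level 2 / level 3: mobility 0.069 / 0.314; self-care 0.104 / 0.214; usual activities 0.036 / 0.094; pain/discomfort 0.123 / 0.386; anxiety/depression 0.071 / 0.236. States are written as five digits in that order.

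**Two readings.**

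- Table: index = 1 - (0.081 × [any answer is 2 or 3] + item decrements + N3)
- Formula line as printed: index = 1 - (0.081 + item decrements + N3)

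**Step 1: the plan's own figure.** For 11111 every condition in the table is false, so the index is 1 - 0 = 1.000. This reproduces the stated maximum. The formula line gives 1 - 0.081 = 0.919.

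**Step 2: which states differ.** There are 3^5 = 243 complete states. Every state except 11111 has at least one 2 or 3, so both readings subtract 0.081. Enumeration of all 243 confirms that 242 agree and one differs, by 0.081. Under the table reading the next-best state is 11211, at 1 - (0.081 + 0.036) = 0.883. The worst is 33333, at 1 - (0.081 + 0.314 + 0.214 + 0.094 + 0.386 + 0.236 + 0.269) = -0.594.

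**Step 3: effect on change to full health.** The Baseline score is the same under both readings unless Baseline is itself 11111, so the loss is always 1.000 - 0.919 = 0.081.

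| Baseline state | Baseline index | Change, table | Change, formula line | Shortfall |
|---|---|---|---|---|
| 11211 (usual activities 2 only) | 0.883 | +0.117 | +0.036 | 0.081/0.117 = 69% |
| 11121 (pain 2 only) | 1 - (0.081 + 0.123) = 0.796 | +0.204 | +0.123 | 0.081/0.204 = 40% |
| 22222 | 1 - (0.081 + 0.403) = 0.516 | +0.484 | +0.403 | 0.081/0.484 = 17% |
| 33333 | -0.594 | +1.594 | +1.513 | 0.081/1.594 = 5% |

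In the 22222 row, 0.403 = 0.069 + 0.104 + 0.036 + 0.123 + 0.071.

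A subject at 11111 at both visits has a change of 0 under either reading. A subject who falls from 11111 has the decline understated by the same 0.081.

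**Step 4: effect on a group mean.** If a proportion p of a group is at 11111 at a visit, the literal formula lowers that group's mean index by 0.081 × p. The documents give no value for p. Over its whole range from 0 to 1, the effect runs from 0 to 0.081.

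**The case against.** The best defence is that the section as a whole shows what is meant. It names Table 14-5 as the value set, the table supplies the missing condition directly below the formula, and SAP 8.3.7 and protocol 9.8 agree on a maximum of 1. An experienced programmer would probably code it correctly. This stands as far as intent goes, and it rules out saying that the plan specifies 0.919 for full health. It does not make the formula line correct: that line is the explicit derivation, and it disagrees with the three other statements.

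A reader might infer more than the documents support, in three ways:

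- **That every subject is scored 0.081 too low.** The constant is subtracted from everyone, but anyone with any problem is due it. Only 11111 is wrong.
- **That the better arm is penalized most.** This would need the proportion of subjects in full health by arm, which the documents do not give. The 40% figure is also specific to one starting state.
- **That the plan scores an unanswered item as no problem, because each decrement is zero when its condition is false.** The column heading of Table 14-5 is ordinary indicator coding for answered items and is not a missing-data rule. For the domain summaries, SAP 8.3.7 counts missing or ambiguous answers in a separate category in the categorical tables and treats ambiguous answers as missing in the numeric ones. What is true is narrower: neither SAP 8.3.7 nor SAP 14.4 gives a missing-item rule for the index, although SAP 4.2.1 refers such rules to the individual sections. That is an omission of detail that analysts would be expected to fill sensibly, and it is noted here only as a minor matter.

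**Conclusion.** The formula line in SAP 14.4 is wrong as written and contradicts Table 14-5, SAP 8.3.7 and protocol 9.8. If it is coded literally, one complete state in 243 is affected: 11111 scores 0.919 instead of 1.000. Improvements that end in full health from any other state, and declines that start from it, are then understated by 0.081.

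The size rests on two assumptions: that the Table 14-5 values are the intended ones, and that the programmer follows the formula rather than the table. The effect on arm means or on the difference between arms cannot be determined from the documents.

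The consequence is limited. SAP 3.1 reserves formal testing for the primary variable, and the index is exploratory and descriptive. The primary analysis is unaffected.

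**What to change.** Rewrite the derivation line in SAP 14.4 as: index = 1 - (0.081 × [any answer is 2 or 3] + item decrements + N3). This returns 1 for 11111, leaves the other 242 complete states unchanged and agrees with Table 14-5. The cost is one edited line and a check that the program gives 1.000 for 11111 and -0.594 for 33333.

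As a separate, optional tidy-up, one sentence could state how the index is handled when an item is missing or ambiguous. Setting it to missing would match the IHS4 rule in SAP 8.3.2, at the cost of slightly more missing index values. Other choices are possible, since the SAP scores or imputes a single missing item for the DLQI and HADS.

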14.5 Hospital Anxiety and Depression Scale

The individual items on the HADS-A and HADS-D scales are listed in [Table 14–6](#).

Table 14–6: Hospital Anxiety and Depression Scale

Each item is scored from 0 to 3, with higher scores indicating more severe anxiety or depression. The total score for HADS-A and HADS-D will be derived by summing the scores over the 7 items and will range from 0 to 21.

In case of missing data, the following rules will be applied:

- If a maximum of 1 item is missing in HADS-A or HADS-D, the missing item will be imputed with the mean score from the remaining completed items within the HADS-A or HADS-D respectively.

- If more than 1 item is missing in HADS-A or HADS-D, the total HADS-A or HADS-D score will not be calculated.

14.6 Treatment-emergent markedly abnormal laboratory values

The criteria for identifying TEMA laboratory values are provided for hematology in [Table 14–7](#) and for chemistry in [Table 14–8](#).

Table 14–7: Definition of TEMA values for hematology

Variable (SI units)	Source	Markedly abnormal definition			
		Low Grade 4	Low Grade 3	High Grade 3	High Grade 4
Hemoglobin (g/L)	RCTC	<70 OR decrease from Baseline of ≥ 30	70 to <80 OR value <LLN and decrease from Baseline of 21 to 29	NA	NA
ALC ($10^9/L$)	CTCAE	<0.2	0.2 to <0.5	NA	NA
ANC ($10^9/L$)	RCTC	<0.5	0.5 to <1.0	NA	NA
WBC ($10^9/L$)	RCTC	<1.0	1.0 to <2.0	NA	NA
Platelets ($10^9/L$)	RCTC	<20	20 to <50	NA	NA

ALC=absolute lymphocyte count; ANC=absolute neutrophil count; CTCAE=Common Terminology Criteria for Adverse Events (CTCAE 2010); LLN=lower limit of normal; NA=not applicable; RCTC=Rheumatology Common Toxicity Criteria; WBC=white blood cell.

Table 14–8: Definition of TEMA values for chemistry

Variable (SI units)	Source	Markedly abnormal definition			
		Low Grade 4	Low Grade 3	High Grade 3	High Grade 4
ALP (U/L)	RCTC	NA	NA	>3.0 to 5.0 x ULN	>5.0 x ULN
ALT (U/L)	RCTC	NA	NA	>3.0 to 8.0 x ULN	>8.0 x ULN
AST (U/L)	RCTC	NA	NA	>3.0 to 8.0 x ULN	>8.0 x ULN
Creatinine ($\mu\text{mol/L}$)	RCTC	NA	NA	>1.8 to 3.0 x ULN	>3.0 x ULN
GGT (U/L)	CTCAE	NA	NA	>5.0 to 20.0 x ULN	>20.0 x ULN
Glucose (mmol/L)	RCTC	<1.67	1.67 to <2.22	>13.89 to 27.78	>27.78

Table 14–8: Definition of TEMA values for chemistry

Variable (SI units)	Source	Markedly abnormal definition			
		Low Grade 4	Low Grade 3	High Grade 3	High Grade 4
Potassium (mmol/L)	RCTC	<2.5	2.5 to <3.0	>6.4 to 7.0	>7.0
Sodium (mmol/L) ^a	RCTC	<120	120 to <125	>155 to 160	>160
Total bilirubin (µmol/L)	RCTC	NA	NA	≥2.0 to 3.0 x ULN	>3.0 x ULN
Calcium (mmol/L)	RCTC	<1.63	1.63 to <1.75	>3.125 to 3.375	>3.375
Cholesterol (total) (mmol/L)	CTCAE	NA	NA	>10.34 to 12.92	>12.92

ALP=alkaline phosphatase; ALT=alanine aminotransferase; AST=aspartate aminotransferase; CTCAE=Common Terminology Criteria for Adverse Events (CTCAE 2010); GGT=gamma glutamyltransferase; NA=not applicable; RCTC=Rheumatology Common Toxicity Criteria; ULN=upper limit of normal.

^a For sodium High Grade 3 and 4 are taken from CTCAE.

14.7 Treatment-emergent abnormal liver values

The criteria for identifying treatment-emergent liver function abnormalities are presented in [Table 14–9](#). Subjects will be counted in all applicable categories for the tabulations ie, a subject with ≥5 x ULN in AST will also be counted in the ≥3 x ULN in AST category, the ≥3 x ULN in AST or ALT category and the ≥5x ULN in AST or ALT category.

Table 14–9: Definition of treatment-emergent liver function values

Criterion
≥3 x ULN increase for AST
≥5 x ULN increase for AST
≥10 x ULN increase for AST
≥20 x ULN increase for AST
≥3 x ULN increase for ALT
≥5 x ULN increase for ALT
≥10 x ULN increase for ALT
≥20 x ULN increase for ALT
≥3 x ULN increase for AST or ALT
≥5 x ULN increase for AST or ALT
≥10 x ULN increase for AST or ALT
≥20 x ULN increase for AST or ALT
≥1 x ULN increase for bilirubin

Table 14–9: Definition of treatment-emergent liver function values

Criterion
≥1.5 x ULN increase for bilirubin
≥1.5 x ULN increase for ALP
≥1 x ULN increase for bilirubin and 3 x ULN increase of either AST or ALT (at the same visit)
≥2 x ULN increase for bilirubin and 3 x ULN increase of either AST or ALT (at the same visit)

ALP=alkaline phosphatase; ALT=alanine aminotransferase; AST=aspartate aminotransferase; ULN=upper limit of normal.

14.8 Treatment-emergent markedly abnormal vital signs values

The criteria for identifying TEMA/PCS vital signs values are provided in [Table 14–10](#).

Table 14–10: TEMA/PCS criteria for vital signs

Variable	Unit	Low ^a	High ^a
Systolic blood pressure	mmHg	Value ≤90 and ≥30 decrease from Baseline	Value ≥180 and ≥40 increase from Baseline
Diastolic blood pressure	mmHg	Value ≤50 and ≥20 decrease from Baseline	Value ≥105 and ≥30 increase from Baseline
Pulse rate	bpm	Value ≤50 and ≥30 decrease from Baseline	Value ≥120 and ≥30 increase from Baseline

bpm=beats per minute.

Note: the change in measurement (increase or decrease) will be calculated relative to the value obtained at Baseline.

^a Both conditions must be satisfied for a measurement to be considered PCS.

14.9 Adverse events for special monitoring

The following AESM are defined for BKZ and will be summarized separately as described in [Section 11.2](#):

- Major cardiovascular events
- Serious infections, including opportunistic infections and TB
- Malignancies including lymphoma
- Cytopenias
- Neuropsychiatric events
- Inflammatory bowel disease
- Anaphylactic reaction (hypersensitivity and anaphylactic reactions)
- Hepatic events and drug induced liver injury

14.9.1 Major cardiovascular events

Major adverse cardiovascular events will be tabulated separately and will be identified using the following UCB defined search criteria:

- All serious TEAEs which code to a PT included in the Scope=Broad and/or Scope=Narrow groups of the following standardized MedDRA queries (SMQ):
 - Haemorrhagic central nervous system vascular disorders
 - Ischaemic central nervous system vascular disorders
- All serious TEAEs which code to a PT included in the HLT = ‘Ischaemic coronary artery disorders’ except events coding to PT = ‘Chest pain’ or PT = ‘Chest discomfort’
- All serious TEAEs which code to a PT = ‘Cardiac failure congestive’

14.9.2 Serious infections, including opportunistic infections and tuberculosis

14.9.2.1 Serious infections

Serious infections are based on MedDRA classification using the SOC = ‘Infections and Infestations’. Such events will be included in the tabulations of SAEs and no separate summary tabulations will be presented.

14.9.2.2 Fungal infections

Fungal infections will be summarized separately based on all TEAEs coding to the high level group term (HLGT) = ‘Fungal infectious disorders’.

14.9.2.3 Opportunistic infections

Opportunistic infections (including TB) will be summarized in a separate table including all TEAEs identified using search criteria defined by UCB.

Opportunistic infections are identified in 2 steps:

- Step 1: Refer to column B of the spreadsheet which identifies the PTs to be classified as opportunistic infections using either a single ‘x’ or a double ‘xx’
 - All TEAEs which code to a PT flagged with a single ‘x’ need to also be serious in order to be considered an opportunistic infection
 - All TEAEs which code to a PT flagged with a double ‘xx’ are considered to be an opportunistic infection, regardless of seriousness.

All serious TEAEs in the study database which code to a PT flagged with a single ‘x’ and all TEAEs in the study database which code to a PT flagged with a double ‘xx’ will be summarized as an opportunistic infection in the stand alone table.

- Step 2: Refer to column C of the spreadsheet which identifies the PTs that need to be evaluated on a case by case basis by the study physician in order to determine whether it is a true opportunistic infection or not. The process for physician review is as follows:
 - Study programming team creates a spreadsheet which lists all of the subjects with a TEAE present in the database which codes to a PT identified as needing case by case

review. Information from the AE dataset to be included in the spreadsheet: Subject ID, AE verbatim term, SOC, HLT, Lower Level Term, PT, AE start date, AE end date, seriousness, severity, relationship to study medication, action taken. Additionally, a column will be included where the study physician can document their decision on the case

- Study physician reviews the cases in the spreadsheet and indicates in the additional column which AEs are confirmed to be opportunistic infections via a single ‘x’
- Study programming team incorporates these decisions into the ADAE dataset by merging the study physician decisions for individual subjects / PTs and flagging the confirmed opportunistic infections as such in the dataset

All subjects with an AE reported that has been confirmed by the study physician to be an opportunistic infection (based on case by case review) will be summarized as such in the stand alone table, together with all of the events identified in Step 1 of this process.

The timing and frequency of Step 2 should be outlined and agreed to by the study team at the beginning of the study.

Following the initial physician review of case by case events, subsequent reviews will be based on the cumulative set of case by case events present in the database at each time point of spreadsheet creation. Physician decisions from previous runs should be retained in each subsequent run. The final run of the spreadsheet, with all study physician decisions on the full set of case by case events, will be archived at the conclusion of the study.

14.9.3 Malignancies including lymphoma

Malignancies will be presented in 2 separate tables based on the following SMQs:

- Malignant or unspecified tumors
- Malignant tumors

Events included in the ‘Malignant tumors’ tabulation will be a subset of the events in the ‘Malignant or unspecified tumors’ tabulation. The SMQ search should include all TEAEs which code to a PT included in the Scope=Narrow group within each SMQ.

The output tables will include 2 different overall incidence rows:

- The first overall incidence row will summarize ‘Any malignancies (including unspecified)’ or ‘Any malignancies’ (depending on the table) and this row will summarize the incidence of all AEs flagged for inclusion in the table, regardless of the HLT it codes to
- The second overall incidence row will summarize ‘Any malignancy (including unspecified, excluding non-melanomic skin cancers)’ or ‘Any malignancy (excluding non-melanomic skin cancers)’ (depending on the table) and this row will summarize the incidence of AEs flagged for inclusion in the table, excluding those which code to an HLT of ‘skin neoplasms malignant and unspecified (excl melanoma)’

14.9.4 Cytopenias

Cytopenias will be tabulated separately based on the SMQ = ‘Haematopoietic cytopenias’. Only serious TEAEs will be included in the tabulation. The SMQ search should include all serious

TEAEs which code to a PT included in the Scope=Broad and/or Scope=Narrow groups within the SMQ.

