11.1.1.4 Adverse events for special monitoring

UCB has identified AEs for special monitoring (AESMs). An AESM is an AE or safety topic for which special monitoring, additional data collection activities, and/or enhanced signal detection activities (within UCB) are considered appropriate. Identified AESM can be of particular concern based on findings from the IMP clinical program to date, potential risks generally associated with biologic immunomodulators, or comorbidities and risk factors prevalent in the study population.

Adverse events for special monitoring for this study include: serious infections (including opportunistic infections and TB, see [Section 11.3.1](#)), cytopenias, hypersensitivities, suicide ideation or behavior (assessed using the C-SSRS), depression and anxiety (assessed using the HADS, see [Section 9.11](#)), major cardiovascular events and liver function test changes/enzyme elevations (ALT, AST, and bilirubin; see [Section 11.2.1](#)), malignancies, and inflammatory bowel diseases.

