14.9.5 Neuropsychiatric events

Neuropsychiatric events (in particular depression, anxiety and suicide ideation or behavior) will be tabulated separately based on the SMQ = 'Depression and suicide/self-injury'. The SMQ search should include all TEAEs which code to a PT included in the Scope=Broad and/or Scope=Narrow groups within the SMQ.

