14.9.7 Anaphylactic reaction

Anaphylactic reactions will be summarized together in a stand alone table with the following incidence rows:

- The first row within the body of the table will be labeled 'Any hypersensitivity/anaphylactic reaction' and will represent the overall incidence of subjects who reported at least 1 hypersensitivity reaction or at least 1 anaphylactic reaction
- The second row within the body of the table will be labeled 'Any hypersensitivity reaction' and will represent the overall incidence of subjects who reported at least 1 hypersensitivity reaction
- The third row within the body of the table will be labeled 'Any anaphylactic reaction' and will represent the overall incidence of subjects who reported at least 1 anaphylactic reaction

Following these three overall incidence rows, all TEAEs that have been identified as either a hypersensitivity reaction or an anaphylactic reaction will be summarized by SOC, HLT and PT (these will not be presented by subcategory).

Hypersensitivity reactions and anaphylactic reactions will be identified as follows:

- **Hypersensitivity reactions:** all TEAEs with onset (start date/time) within 24 hours after any administration of IMP, which code to a PT which contains the term 'hypersensitivity' will be considered to be a hypersensitivity reaction and included in the summary table
- **Anaphylactic reactions:** An algorithmic approach will be used to identify TEAEs that are considered to be anaphylactic reactions. Preferred terms are separated into 4 distinct categories (A, B, C, D) prior to the algorithmic approach being applied.

All TEAEs with onset (start date/time) within 24 hours after any administration of IMP, and which fulfill any of the 3 criteria described in [Section 14.9.7.1](#) will be included in the summary table.

Any TEAEs with missing start time will be assumed to have occurred at the time of or after dosing for this purpose, if the event date is on the same day as a dosing date.

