5. Cardio respiratory arrest
6. Cardiovascular insufficiency
7. Diastolic hypertension
8. Hypotension

- An **algorithmic approach**: If a subject reports any TEAE which codes to a PT included in Category D **AND** reports (either a TEAE which codes to a PT included in Category B **OR** a TEAE which codes to a PT included in Category C), **and both TEAEs have the same start date**, then both events will be flagged as anaphylactic reactions and summarized as such in the table

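### Three special-monitoring searches in SAP 14.9 (cytopenias, anxiety, hypersensitivity) do not deliver the groups they are meant to report, and one anaphylaxis trigger term looks wrong

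*SAP*

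**What the plan says.** Protocol 11.1.1.4 lists the topics for special monitoring, among them "cytopenias, hypersensitivities, suicide ideation or behavior (assessed using the C-SSRS), depression and anxiety (assessed using the HADS". The word serious is attached to infections only. No time limit is set for hypersensitivities.

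The SAP makes these topics operational in section 14.9:

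- **Cytopenias (14.9.4).** The haematopoietic cytopenias query is used in broad and narrow scope, with the restriction "Only serious TEAEs will be included in the tabulation".
- **Neuropsychiatric events (14.9.5).** "Neuropsychiatric events (in particular depression, anxiety and suicide ideation or behavior) will be tabulated separately based on the SMQ = 'Depression and suicide/self-injury", in broad and narrow scope. No other query, term group or term list is given.
- **Hypersensitivity (14.9.7).** The row counts "all TEAEs with onset (start date/time) within 24 hours after any administration of IMP, which code to a PT which contains the term 'hypersensitivity".
- **Anaphylaxis (14.9.7 and 14.9.7.1).** "An algorithmic approach will be used to identify TEAEs that are considered to be anaphylactic reactions". A Category A term counts alone. A Category B term counts with a Category C term of the same start date. A Category D term counts with a Category B or C term of the same start date. All of these must start within 24 hours of a dose. Category D includes "Diastolic hypertension".

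**The concern.** A special-monitoring table exists to gather related preferred terms into one count per arm. In arms of about 20 and 40, single events spread over different preferred terms do not add up to anything visible, and a zero in the grouped row will be read as no signal. If the search leaves out events that belong to the topic, that zero is not informative. If a trigger term is wrong, the table can also show an anaphylaxis case that is not one.

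Cytopenia deserves some care here. Protocol 2.2.1 reports a slight fall in mean neutrophil count on active drug in the earlier psoriatic arthritis study. The protocol calls that fall not clinically relevant and finds no clear relationship with dose or time, so it is a reason to group such events by arm, not evidence of harm.

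**Working it through.** There is no sample size, power or event figure to reproduce. The check runs test events through the rules as written.

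| Test event (TEAE) | Special-monitoring table | Other output |
|---|---|---|
| Non-serious neutropenia, ANC below 1.0 × 10⁹/L | Not in the cytopenia table | Grade 3/4 laboratory table (SAP Table 14–7: 0.5 to <1.0, and <0.5); neutrophil shift table; general TEAE tables |
| Non-serious, related Grade 2 blood event lasting 28 days or more, laboratory values staying outside the Table 14–7 limits | Not in the cytopenia table | Not in the Grade 3/4 laboratory table; in the general TEAE tables |
| Anxiety alone | No anxiety-specific search is specified | General TEAE tables; HADS-A scores summarized separately (SAP 8.3.10) |
| Urticaria or angioedema alone, within 24 hours of a dose | No row: the word is absent, and a Category C term needs a partner | General TEAE tables |
| Term containing hypersensitivity, starting after 24 hours | No row | General TEAE tables |
| *Diastolic hypertension* plus *Cough*, same start date, within 24 hours of a dose | Flagged as anaphylactic reaction (D + B) | General TEAE tables |

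**Cytopenias.** The second row of the table is the one that matters. Protocol 6.3, criterion 9, makes a persistent, related Grade 2 event in the blood and lymphatic class a reason to withdraw IMP. Protocol 6.4.1 counts criterion 9 among those for which more than one affected subject brings the DMC together. Such an event need not meet an SAE criterion. One caution: criterion 9 uses CTCAE grades, while Table 14–7 uses mostly RCTC grades. Some hemoglobin falls that are Grade 2 on one scale may therefore still reach the laboratory table, which is why the test event is conditioned on the laboratory value.

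**Anxiety.** SAP 14.9.5 names anxiety as a target, and Protocol Table 11–1 lists Anxiety as a preferred term separate from Depression. The only query specified is titled for depression and suicide/self-injury. Its term list is not in the documents, so the supportable statement is that no anxiety-specific search is given.

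**The 24-hour rule.** Inputs: 9 dosing visits (Protocol 7.2: Baseline and Weeks 2, 4, 5, 6, 7, 8, 9 and 10), last dose at Week 10 (day 70), and a TEAE window to 140 days after the last dose (SAP 11.2).

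- Time covered by the rule: 9 × 1 day = 9 days.
- TEAE window: 70 + 140 = 210 days, so 9 / 210 = 4.3%.
- Treatment Period: 84 days, so 9 / 84 = 10.7%.

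These are shares of calendar time, not of events. Reactions may well cluster after injections, so the share of events missed could be much smaller.

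**Category D.** Of its 8 terms, 7 describe low pressure, arrest or circulatory insufficiency; *Diastolic hypertension* is the eighth. It can pair with any of 39 Category B or 29 Category C terms, so 39 + 29 = 68 pairings would raise an anaphylaxis flag.

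**Size of one misplaced subject.** 1 / 20 = 5 percentage points (placebo or adalimumab); 1 / 40 = 2.5 percentage points (bimekizumab).

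**The case against.** The case against is substantial, and much of it stands.

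- **Nothing is lost.** SAP 11.2 tabulates every TEAE by arm, SOC, HLT and PT, and also by relationship and maximum intensity. The AE listings give days since the most recent dose. A reader might infer that a lone urticaria is counted nowhere; the documents do not support that.
- **Marked neutropenia is covered.** A reader might infer that a neutropenia forcing withdrawal under criterion 6 goes unreported. It does not: the neutrophil and lymphocyte limits in criterion 6 are the Grade 3 limits in SAP Table 14–7, tabulated regardless of seriousness, and neutrophil shift tables and mean plots are added.
- **No protocol-defined analysis was altered.** A reader might infer that SAP 3.9 should list these limits. Protocol 11.1.1.4 describes monitoring topics, and the safety analysis section (15.8) prescribes no special-monitoring tables. SAP 14.9 supplies the first definitions, so there was nothing for 3.9 to record.
- **The anxiety query's contents are unseen.** Its broad scope may contain some anxiety terms, and HADS-A is summarized at each visit.
- **Category C is noisy.** Counting all 29 terms unpaired would bring in erythema, swelling, oedema and nodular rash in an inflammatory skin disease where erythema is itself scored. Protocol 6.3.1 does list rash as a hypersensitivity symptom, but only in its liver rules.
- **Low stakes for the primary result.** No success criterion uses these tables, and the DMC works from its own SAP.

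What these arguments leave untouched is narrower. The cytopenia table omits non-serious events that the protocol treats as reasons to stop IMP. The SAP promises anxiety without saying how it is found. The hypersensitivity row depends on one word and one day. One Category D term runs opposite to its neighbours.

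**Conclusion.** The point holds as a specification weakness in three named searches plus one doubtful trigger term. Followed as written, the rules give incomplete grouped tables for cytopenias and hypersensitivity, leave anxiety without a stated search, and allow a false anaphylaxis flag. The last runs towards over-capture, the others towards under-capture. It should not be read as a criticism of every special-monitoring search: fungal infections, for instance, are searched regardless of seriousness (SAP 14.9.2.2).

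The size is one subject at a time, 5 or 2.5 percentage points by arm. The number of events affected cannot be derived from the documents and may be zero. The conclusion assumes that the programmer implements section 14.9 literally and that the events concerned are coded to the terms shown. The treatment comparison on HiSCR is not affected.

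**What to change.** In SAP 14.9:

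1. **14.9.4:** tabulate all TEAEs in the cytopenia query, with serious events as a sub-row. The malignancy tables in 14.9.3 already use two overall incidence rows.
2. **14.9.5:** add a named anxiety search, shown as its own row.
3. **14.9.7:** add one row for clearly allergic unpaired terms within 24 hours of a dose (for example angioedema, urticaria, injection site urticaria and allergic oedema), and one for terms containing hypersensitivity that start later. Leave out erythema, swelling, oedema and rash, which overlap with the disease.
4. **14.9.7.1:** remove or correct *Diastolic hypertension* in Category D.

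If the sponsor intends any of the first three limits, a sentence of justification in the SAP would do instead. The fourth needs a correction or an explanation.

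The cost is SAP wording and a few table rows built from coded data already held. The downside is that the new rows include milder events; the separate rows keep these apart from the existing counts.
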